10.3 POPULATIONS FOR ANALYSIS

Modified intention to treat: all participants who receive at least one dose of the two vaccines and the immune checkpoint inhibitor will be included in the statistical analyses performed. The lead-in cohort will be evaluated separately in a descriptive fashion and for safety primarily.

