2.3.1 Treatment Assignment Procedures (for registration purposes only)

Cohorts

Number	Name	Description
1	Lead-In Cohort (closed December 2018)	Participants with advanced castration resistant prostate cancer (first six participants)
2	Biochemical Recurrence Cohort	Participants with biochemically recurrent prostate cancer

Arms

Number	Name	Description
1	Combination therapy (closed December 2018)	Prostvac + CV301 + MSB0011359C
2	Combination therapy + surveillance (closed)	Surveillance followed by Prostvac + CV301 then Prostvac + CV301 + MSB0011359C
3	Combination vaccine therapy +/- surveillance	Surveillance as needed followed by Prostvac + CV301

Arm Assignment

Participants in cohort 1 will be directly assigned to Arm 1 of the study. This cohort has been closed as of December 2018.

Participants in cohort 2 will be directly assigned to Arm 2, or Arm 3 of the study based upon time of enrollment. Participants enrolling after approval of amendment dated 7/29/2021 are assigned to Arm 3.

Please note: As of December 21, 2018, the 6 participants in the lead in cohort have completed the 6-week toxicity assessment period and no SAEs were seen. Per the protocol design participants will now be enrolled to the BCR cohort. The toxicity assessment of participants in the lead-in cohort is described in section [1.2.13](#).

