3 STUDY IMPLEMENTATION

3.1 STUDY DESIGN

This is a three-arm, open-label trial of combination immunotherapy in participants with biochemical recurrent prostate cancer. 37 evaluable participants will be enrolled (after the Safety Lead-In cohort with 6 participants (arm 1), 6 participants who received M7824 as part of the initial investigation for PSA response (arm 2), and 25 homogenously treated participants (arm 3) with an accrual ceiling of 40 participants.

A 6-participant phase I lead in cohort in advanced castration resistant prostate cancer participants will be conducted to determine safety. Dose levels for the lead in cohort are equivalent to the biochemical recurrence cohort. Participants will not have an observation period for the safety lead-in; dosing will begin after eligibility is confirmed (see Study Calendar in Section **18.2**).

Once all 6 participants have completed a 6-week toxicity assessment period the toxicity data will be shared with IRB before moving forward with the planned study in biochemical recurrence.

Participants may remain on treatment with vaccines in the lead in cohort as long as the participant is willing and their disease remains stable on follow-up imaging. As of December 21, 2018, the 6 participants in the lead in cohort have completed the 6-week toxicity assessment period and no SAEs were seen; therefore this cohort is closed.

Participants enrolled in Cohort 2 will undergo surveillance with four consecutive monthly PSA checks followed by Prostvac and CV301 during months 1-4 then Prostvac and CV301 during months 5-7.

- Existing participants with biochemical recurrent prostate cancer undergoing surveillance and PSA monitoring at the NIH may be enrolled at any point during the surveillance period provided the PSA monitoring is consistent with PSA monitoring in the Study Calendar (**APPENDIX C**) and the participant meets all other eligibility criteria. For example, if an eligible participant has 3 monthly PSA values, he may be enrolled onto the study, obtain one additional PSA value at a one month interval to complete the surveillance period, then

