begin C1D1 with vaccine therapy. In this case, the 3 PSA values obtained prior to enrollment will be evaluated as if they were collected during the surveillance period while enrolled and will factor into the determination of the intra-study apex value (See Section 6.3.2) highest PSA that is within 10% of another peak PSA for the participant on-study. Any other peak PSA values that are beyond 10% of other PSA values on the study will be determined as potential lab variability and excluded from response assessment.

- With Amendment v05/10/2023, participants that have at least 3 PSA measurements in the surveillance period, with at least one of them sufficient to provide the doubling time from baseline, will not undergo any further PSA measurements in the surveillance period.

Prostvac will be administered nearly identical to the Phase III dosing with Prostvac-V given day 1 (week 1) followed by Prostvac-F on weeks 3 and 5 then monthly for an additional 5 months. Therefore, Prostvac-V is given one time (priming vaccine) followed by 7 doses of Prostvac-F (booster vaccine). The administration schema for CV301 is representative of the Phase I dose escalation trial. MVA-BN-CV301 (priming vaccine) is administered on day 1 (week 1) and week 3 followed by FPV-CV301 (booster vaccine) administered on week 5 then monthly for an additional 5 months.

MSB0011359C (anti-PDL1 TGF β Trap) will be administered at the recommended phase II dose of 1200mg by IV infusion every 2 weeks for 3 months (6 doses) starting after 4 months of concurrent Prostvac and CV301.

Effective with amendment v7/29/2021, MSB0011359C will no longer be given as part of the treatment combination for the Biochemical Recurrence cohort (Arms 2 and 3). This cohort will now receive Prostvac and CV301 during months 1-7 following surveillance.

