10.2 SAMPLE SIZE DETERMINATION

The trial will begin with a 6-participant safety lead-in. Following determination of safety, the primary objective of this study is to determine if the use of two vaccines combined with an immune checkpoint inhibitor can be associated with a modestly high fraction of participants who can experience at least a 30% decline from their maximum PSA anytime during treatment to the minimum value during treatment.

Safety data for the 6-participant lead-in will be shared with IRB before accrual commences in the biochemical recurrence cohort. Beyond safety, this cohort will just be evaluated in a descriptive manner.

Because participants may be receiving the proposed treatment and be followed for PSA changes over an extended period, and the evaluation of the endpoint may take place at any point during this potentially long period, the trial will use a single stage design for evaluating efficacy. With 25 evaluable participants who do not receive M7824, there would be 82% power to rule out 15% and be consistent with 35% who may be able to experience a 30% decline in PSA, using an exact binomial test with a 0.10 one-sided significance level. As an illustration, if 25 evaluable participants are enrolled, 7 of 25 (28.0%) who experience at least a 30% PSA change from the maximum level would have an associated one-sided lower 90% confidence interval bound of 16.3%, and simultaneously an associated one-sided upper 90% confidence interval bound of 42.6%. These demonstrate that 7/25 would be a desirable result based on the parameters selected.

With the amendment v7/29/2021, the initial 6 participants who received M7824 will be evaluated separately in exploratory fashion and will not be included among the 25 main participants.

In addition, because a trial of participants with similar eligibility (16-C-0035) may result in approximately 36 participants who are undergoing surveillance for 6 months, this other trial may serve as a control for a secondary evaluation. The changes in PSA on this trial during the initial 6 months can be compared to the changes in PSA during the initial 6 months on the surveillance arm of the control trial as a secondary evaluation. With 25 evaluable participants on this trial and 36 evaluable participants on the other trial, there would be 81% power to identify a difference between 35% of participants on this trial with a 30% PSA maximum change and 10% of participants on the

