10.4.2 Analysis of the primary efficacy endpoints

The fraction of evaluable participants who experience at least a 30% decline from the maximum to the minimum PSA value while on study will be determined. A two-tailed 80% and 95% confidence interval will be formed around the fraction of participants with 30% decline to interpret the fraction who experience a decline of that magnitude. This primary analysis will not include the 6 patients who received M7824 before it was removed from future use in this study.

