Rash		2 (0.3)

Source: ADSL 23DEC2020 8:38, ADAE 23DEC2020 9:27, OutputID:T-39-aefrq.

SAR = serious adverse reactions.

The important potential risks include hypersensitivity, irAEs/autoimmune disorders, anemia, rash with hyperkeratosis/keratoacanthomas/SCC of the skin, embryo-fetal toxicity, and impaired wound healing. The important identified risks with binrafusp alfa observed to date were overall manageable. Mucosal bleeding events of mild to moderate severity were observed in participants treated with binrafusp alfa in ongoing studies and are a potential risk for binrafusp alfa. Events may include epistaxis, hemoptysis, gingival bleeding or hematuria amongst others. In general, these reactions resolve without discontinuation of treatment.

In addition, after discussion among NCI investigators on multiple protocols using M7824, multiple bleeding events ranging from low grade gingival bleeding and epistaxis to more serious hemoptysis, GI bleeding and hematuria have been observed. Some of these events can be attributed to bleeding events related to cancer directly and others bleeding events can be attributed to colitis or cystitis which is a known toxicity of anti-PD-L1 agents including M7824. However, there remains the possibility that M7824 may increase the overall risk of bleeding in ways that may not be directly related to direct tumor bleeding or inflammatory bleeding events described with checkpoint inhibitors like M7824. It is hypothesized that this possible increased bleeding risk may be due to TGF beta inhibition which has an effect on angiogenesis; bleeding has also been observed in participants receiving M7824 and may be drug-related (e.g., gum bleeding, nose bleeds, coughing up blood, blood in their urine, or blood in the stool). Accordingly, participants will be notified of the same possible risk in the informed consent document for this study.

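### Section 10.3 still requires a dose of the checkpoint inhibitor: read literally it leaves no one for the primary analysis, and no valid inclusion rule stands in its place

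*Combined protocol and SAP*

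**What the plan says.** The regimen contains one checkpoint inhibitor, MSB0011359C, also called M7824. Section 14.4.2 classes it that way in speaking of "checkpoint inhibitors like M7824". Section 3.1 records that, with amendment v7/29/2021, the drug is no longer given to the BCR cohort. Section 2.3.1 describes the Arm 3 regimen as "Surveillance as needed followed by Prostvac + CV301".

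The statistical sections treat this change unevenly:

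- **10.3** defines a single modified intention-to-treat population: "all participants who receive at least one dose of the two vaccines and the immune checkpoint inhibitor will be included" in the analyses. It sets the lead-in cohort apart for descriptive and safety evaluation.
- **10.4.2** states: "This primary analysis will not include the 6 patients who received M7824 before it was removed from future use in this study".
- **10.2** opens with a primary aim to "determine if the use of two vaccines combined with an immune checkpoint inhibitor can be associated with a modestly high fraction" of participants with a PSA decline. It then bases the power on 25 evaluable participants who do not receive M7824, and says that the 6 recipients are evaluated separately.
- **3.1** gives the size as "25 homogenously treated participants (arm 3) with an accrual ceiling of 40 participants", after 6 in Arm 1 and 6 in Arm 2.
- **10.4.1 and 10.4.2** take the fraction of *evaluable* participants with a decline of at least 30%. No section defines that word.
- **10.4.3** still plans PSA slopes after the checkpoint inhibitor.

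**The concern.** Sections 10.2 and 10.4.2 were revised when M7824 was withdrawn, but 10.3 was not. As it stands, the population section admits the people whom the primary analysis excludes, and leaves out the people on whom it depends.

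Once 10.3 is set aside as unworkable, the other sections supply a target number (25) and an exclusion (M7824 recipients), but no rule for who is in. The denominator could be everyone enrolled in Arm 3, everyone with any dose, everyone dosed with both vaccines, or everyone with enough PSA values. The trial is open-label and single-arm, and its primary result is a simple proportion. A denominator settled after PSA results are known is open to challenge.

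**Working it through.** **1. The plan's own figures.** Inputs from 10.2: n = 25, null rate 0.15, target rate 0.35, exact binomial test, one-sided level 0.10.

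- Critical value: the smallest r with P(X ≥ r | 25, 0.15) ≤ 0.10. P(X ≥ 6) = 0.162 and P(X ≥ 7) = 0.070, so r = 7.
- Power: P(X ≥ 7 | 25, 0.35) = 0.827. The plan states 82%, so this reproduces.
- One-sided 90% Clopper-Pearson bounds for 7/25: the lower is the 0.10 quantile of Beta(7, 19), 16.3%; the upper is the 0.90 quantile of Beta(8, 18), 42.6%. Both reproduce.
- Secondary Fisher comparison, 25 vs 36, 35% vs 10%, one-sided 0.10, by full enumeration: power 0.814. The plan states 81%, so this reproduces.

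The numbers are therefore right for 25 participants without M7824.

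**2. Who satisfies 10.3.** Arm sizes are from 3.1 and 10.2, regimens from 2.3.1.

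| Group | n | Both vaccines | M7824 | Meets 10.3 as worded | Position in the primary analysis |
|---|---|---|---|---|---|
| Arm 1, lead-in | 6 | yes | yes | yes | separate (10.3) |
| Arm 2 | 6 | yes | yes | yes | excluded (10.4.2) |
| Arm 3 | 25 | yes | no | **no** | intended (10.2), not admitted by 10.3 |

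Members of the 10.3 population left for the primary analysis: 12 − 6 − 6 = 0. Arm 3 participants admitted: 0 of 25.

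**3. Whether the missing rule can change the answer.** The ceiling is 40 (3.1, 10.2). With 6 in Arm 1 and 6 in Arm 2, Arm 3 can hold up to 40 − 6 − 6 = 28. Take 7 responders and let the denominator run from 25 to 28. Here p = P(X ≥ 7 | n, 0.15), and the lower one-sided 90% bound is the 0.10 quantile of Beta(7, n − 6).

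| n counted | p for 7 responders | Lower 90% bound | Responders needed at 0.10 | Power at 35% with that threshold |
|---|---|---|---|---|
| 25 | 0.070 | 16.3% | 7 | 0.827 |
| 26 | 0.083 | 15.7% | 7 | 0.858 |
| 27 | 0.099 | 15.1% | 7 | 0.885 |
| 28 | 0.115 | 14.5% | 8 | 0.818 |

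At n = 25, 26 or 27, seven responders rule out 15%. At n = 28 they do not. With seven responders the conclusion reverses only if all three spare places are filled and all three participants are counted.

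**The case against.** The best reply is that the intent is plain. Section 10.2 names its population, 10.4.2 repeats the exclusion, 3.1 and 10.2 both list 6 + 6 + 25, and 10.4.9 makes the M7824 recipients descriptive. No one could run an analysis on an empty set, so in practice the 25 would be analysed. Section 10.3 also says who will be included and does not use the word *only*. Most of this stands: the empty set follows from the literal text and is not a forecast. It does not rescue 10.3, because a modified intention-to-treat definition is normally read as exclusive, and the sections that show the intent supply no minimum-dose rule and rely on an undefined word.

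A reader might also infer three stronger things that the documents do not support:

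- *That the 82% power is unsound.* It is not. The sentence in 10.2 states its own population, and the figure reproduces.
- *That the safety fractions would omit Arm 3.* Section 10.4.4 reports adverse events for each participant and does not invoke the 10.3 population. Naming a safety set would be clearer, but the present text does not remove Arm 3 from safety reporting.
- *That some Arm 2 participants have no place in any analysis.* Section 2.3.1 assigns arms by enrolment time, for registration only, whereas 10.2 and 10.4.2 select by receipt of M7824, which began after four months of vaccines. Someone could in principle be in Arm 2 without reaching it. But 3.1 describes Arm 2 as 6 participants who received M7824, and nothing shows that such a person exists.

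Nor is the trial's question misstated throughout. The objectives in 1.1.1 and 10.1.1 speak of combination immunotherapy, which fits two vaccines. The opening aim in 10.2 and the slope wording in 10.4.3 are what remain out of date.

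**Conclusion.** The contradiction is real and should be corrected before the primary analysis. The only population definition in the current version excludes all 25 participants for whom the primary analysis was designed, and 10.4.2 removes the BCR participants whom it does admit. The likely cause is text not updated when M7824 was withdrawn.

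The practical damage is narrower than an empty analysis. The sample size, test, power and illustrative bounds all stand. What is lacking is a valid inclusion rule and a meaning for *evaluable*. At the margin that gap decides the result: 7 responders succeed with 25 to 27 counted and fail with 28. This rests on two assumptions: that Arms 1 and 2 hold exactly 6 each, as 3.1 states, and that accrual reaches the ceiling of 40. If Arm 3 closes at 25, there is no larger denominator to dispute, but the written rule is still wrong.

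**What to change.** - **10.3, primary efficacy set:** all BCR participants not given M7824 who receive at least one dose of Prostvac and at least one dose of CV301. This keeps the selection by drug received that 10.2 and 10.4.2 already use.
- **'Evaluable':** give it this meaning in 10.2, 10.4.1 and 10.4.2. A dosed participant without usable later PSA values then stays in the denominator and is not a success; the text should say so.
- **Threshold:** because the final number may differ from 25, state the responders needed at each possible size: 7 for 25 to 27, and 8 for 28.
- **Other sets:** state that M7824 recipients and the lead-in cohort are each analysed separately and descriptively, and that safety covers everyone who receives any study agent, by arm.
- **Arm 2:** if any Arm 2 participant never received M7824, state in advance where he is counted.
- **Leftover wording:** align the opening aim in 10.2 and the checkpoint-inhibitor slopes in 10.4.3 with the two-vaccine regimen.

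The cost is a wording amendment. Sample size, test, visits and data collection do not change.

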10.4 STATISTICAL ANALYSES

10.4.1 General approach

Following a safety determination in 6 participants meeting separate eligibility requirements, the PSA decline measured from the maximal value obtained while on study to the minimum value obtained while on study will be obtained for each patient, and will be considered a success if the maximal PSA decline is 30% or more. The fraction of evaluable participants who experience at least a 30% decline will be determined. Quantitative parameters will be tested for changes over time using paired tests.

10.4.2 Analysis of the primary efficacy endpoints

The fraction of evaluable participants who experience at least a 30% decline from the maximum to the minimum PSA value while on study will be determined. A two-tailed 80% and 95% confidence interval will be formed around the fraction of participants with 30% decline to interpret the fraction who experience a decline of that magnitude. This primary analysis will not include the 6 patients who received M7824 before it was removed from future use in this study.

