control trial with a 30% PSA maximum change with a 0.10 one-sided significance level Fisher's exact test.

It is anticipated that 1-2 participants per month can be enrolled onto this trial; thus, it is expected that accrual of 37 evaluable participants (6 for the lead-in, 6 who received M7824 as part of the initial investigation for PSA response and 25 homogeneously treated participants to evaluate PSA response) can be completed within 1 to 2 years. To allow for a small number of inevaluable participants, the accrual ceiling will be set at 40 participants.

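### The primary response fraction is taken over an undefined evaluable group, and the only defined analysis set (10.3) cannot apply to the 25 primary participants; the effect on the conclusion is limited to a borderline result

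*Combined protocol and SAP*

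**What the plan says.** Three parts of section 10 bear on the denominator.

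- **10.4.1 and 10.4.2** define the primary result as "The fraction of evaluable participants who experience at least a 30% decline", measured from the highest to the lowest on-study PSA. The six men who received M7824 are excluded from it.
- **10.2** sizes the trial on the same term: "With 25 evaluable participants who do not receive M7824, there would be 82% power to rule out 15% and be consistent with 35"%, "using an exact binomial test with a 0.10 one-sided significance level". It adds, after giving a target of 37 evaluable participants (6 lead-in, 6 with M7824, 25 main): "To allow for a small number of inevaluable participants, the accrual ceiling will be set at 40 participants".
- **10.3** defines the only analysis population, a modified intention-to-treat set for the statistical analyses: "all participants who receive at least one dose of the two vaccines and the immune checkpoint inhibitor will be included".

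No section defines evaluable for PSA response or says how a dosed man with too few PSA values is counted. Sections 2.3.1 and 3.1 say that Arm 3 receives Prostvac and CV301 only, MSB0011359C (M7824) having been dropped for the biochemical recurrence cohort with the amendment of 7/29/2021.

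**The concern.** Two denominators are on the page and neither can be applied as written. The evaluable group has no definition. The 10.3 set has one, but it was not updated when the checkpoint inhibitor was removed, so no Arm 3 participant can meet it.

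The gap matters because this is a single-arm, open-label test of a proportion against a fixed 15%. If a dosed man is ruled inevaluable because his PSA series is too short, he leaves the denominator and cannot count as a non-responder. A responder, by contrast, must have enough values to show the decline. Exclusions of this kind can therefore push the observed fraction up and not down. Without a rule fixed in advance, the decision about who is evaluable could also be made with PSA results in view.

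The plan also gives two response definitions. Section 6.3.2 asks for an apex PSA supported by another value within 10%, followed by at least two consecutive later values showing the decline. Sections 10.4.1 and 10.4.2 use the simple fall from maximum to minimum. How many PSA values a man needs in order to be evaluable depends on which of these is meant.

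**Working it through.** **Inputs**

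- Null rate 15%, target rate 35%, n = 25, exact binomial test, one-sided 0.10, stated power 82% (10.2).
- The plan's illustration of a desirable result: "7 of 25 (28.0%) who experience at least a 30% PSA change from the maximum level", with a "one-sided lower 90% confidence interval bound of 16.3"% and an upper bound of 42.6% (10.2).
- Accrual ceiling 40 and evaluable target 37 (10.2, 3.1).

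**Step 1. Reproduce the design.** The cut-off is the smallest r with P(X ≥ r | n = 25, 0.15) ≤ 0.10.

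- r = 6 gives 0.1615, which is too large.
- r = 7 gives 0.0695, so the cut-off is 7.
- Power = P(X ≥ 7 | 25, 0.35) = 0.827, against the stated 82%.
- The exact (Clopper-Pearson) one-sided 90% bounds for 7/25 are 16.3% and 42.6%, as stated.

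The plan's own figures hold.

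**Step 2. Room for exclusions.** 40 − 37 = 3 places beyond the target. If all three fall in Arm 3, the number dosed there is at most 25 + 3 = 28. The documents do not give the actual number of excluded dosed men, so I take the range 0 to 3.

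**Step 3. Put the excluded men back as non-responders.** Hold the responders at 7 and test against 15%, with p = P(X ≥ 7 | n, 0.15).

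| Excluded dosed men | Fraction | p | Lower 90% bound | Rules out 15%? |
|---|---|---|---|---|
| 0 | 7/25 = 28.0% | 0.0695 | 16.3% | yes |
| 1 | 7/26 = 26.9% | 0.083 | 15.7% | yes |
| 2 | 7/27 = 25.9% | 0.0986 | 15.05% | yes, barely |
| 3 | 7/28 = 25.0% | 0.115 | 14.5% | no |

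The p column is also the type I error of keeping a cut-off of 7 when n men were dosed and the excluded men are all non-responders. It passes 0.10 only at n = 28, where it is 0.115.

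**Step 4. Cut-off for the actual n.** It stays at 7 for n = 25 to 27. At n = 28 it becomes 8, with P(X ≥ 8 | 28, 0.15) = 0.049. Eight responders of 28 would therefore still rule out 15%.

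**Step 5. Power after the change.**

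- At n = 28 with cut-off 8, if all 28 men respond at 35%: P(X ≥ 8 | 28, 0.35) = 0.818.
- If 25 men respond at 35% and the three added men are all non-responders: P(X ≥ 8 | 25, 0.35) = 0.69.
- At n = 26 or 27 with cut-off 7, if the one or two added men are non-responders: P(X ≥ 7 | 25, 0.35) = 0.827, unchanged from the plan.

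**The case against.** A reader might infer that the plan removes early failures from the denominator and replaces them. The documents do not support that reading.

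- **Replacement is not stated.** Section 10.2 sets a ceiling and gives its purpose. It has no replacement rule, and the three spare places are not tied to Arm 3.
- **Early stoppers would mostly remain measurable.** The study calendar (18.1) takes PSA at screening, baseline, up to four surveillance visits, C1D1, C1D15 and each later cycle. Section 3.1 lets surveillance values count towards the apex. Progression or toxicity ends treatment (3.6.1) but is not listed as a reason to leave the study for this cohort (3.6.2), and follow-up continues monthly for five months (3.7). Of the usual reasons for stopping early, only ADT takes a man off study, and his earlier values remain.
- **Under 10.4.1 and 10.4.2 very few values are needed.** The confirmation requirement is in 6.3.2, not in the analysis section.
- **The spare places may be for undosed men.** Enrolment comes before surveillance, so some men may leave without a dose. An all-dosed denominator would omit them too, and n would stay at 25.
- **Evaluable might simply mean the 10.3 set.**

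The first four points stand, and they limit the claim to what the wording permits rather than what it will produce. The last does not rescue the plan: read literally, the 10.3 set has no Arm 3 members, so it cannot supply the missing definition.

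**Conclusion.** The point holds in a limited form. The primary denominator is undefined, it differs from the set in 10.3, and 10.3 cannot be applied to the primary group because of its checkpoint-inhibitor requirement. The wording allows up to three dosed Arm 3 men to drop out of the denominator, and any such exclusion for too few PSA values can bias the fraction upward.

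At 7 responders the estimate moves from 28.0% to between 26.9% and 25.0%. A reader might infer that a negative trial could generally be turned into a positive one. That is too strong. With 7 responders the conclusion changes only if all three spare places are used by dosed, excluded Arm 3 men. With one or two exclusions it stands, and with 8 or more responders it stands even at n = 28. The worst type I error is 0.115 against the stated 0.10. Still, 7/25 is the plan's own example of a desirable result and equals the 28% in the primary objective, so the borderline case is worth settling in advance.

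These figures assume that the excluded men were dosed, that they count as non-responders, and that there are between 0 and 3 of them. The documents confirm neither who would be excluded nor how many.

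**What to change.** - **10.3:** define the primary population as every Arm 3 participant who received at least one dose of each vaccine, and delete the checkpoint-inhibitor requirement for this group.
- **10.2, 10.4.1 and 10.4.2:** use that set as the primary denominator. Count anyone without a qualifying PSA decline, including those with too few PSA values, as a non-responder. Say whether qualifying means the confirmed decline of 6.3.2 or the maximum-to-minimum fall.
- **10.2:** state the exact cut-off for the actual n: 7 for n = 25 to 27, 8 for n = 28.
- **Sensitivity analysis:** report the evaluable-only fraction, with evaluable defined before the primary analysis and the excluded men listed with reasons.

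The cost is wording, with no added visits or participants. The observed rate may be slightly lower. If 28 men are dosed, power is 81.8% provided the added men respond at 35%, but about 69% if all three are non-responders. The change is therefore not free in that case, and the plan should say so.

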6.3.2 Intra-study PSA response

Participants will be monitored for PSA kinetics once enrolled. Participants who have an intra study decline in PSA will be evaluated for PSA response. Such responses would be defined by an intra-study apex PSA, which will be established by determining the maximum PSA value that can be validated by another intra-study PSA value within 10%. (The goal here is to not capture lab variations which may be seen as isolated PSA spikes (i.e. greater than 10%) in the context of participant follow-up. Responders will then be evaluated using confirmed PSA declines (at least 2 consecutive values after the intra-study apex) of at least 30%. Participants with intra-study PSA declines greater than 50% will also be identified.

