10 STATISTICAL CONSIDERATIONS

10.1 STUDY OBJECTIVES

10.1.1 Primary

The primary objective is to determine if the combination immunotherapy can result in a confirmed 30% decline in PSA in a modest fraction of participants enrolled

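### The primary PSA response is defined inconsistently: sections 10.4.1 and 10.4.2 require neither the confirmation, the apex validation nor the explicit time order that section 6.3.2 requires, and the assessment windows differ.

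*Combined protocol and SAP*

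**What the plan says.** The combined protocol and SAP describes the primary response in several places.

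- **Section 10.4.1** bases success on "the PSA decline measured from the maximal value obtained while on study to the minimum value obtained while on study"; a participant "will be considered a success if the maximal PSA decline is 30% or more".
- **Section 10.4.2**, the primary analysis, takes the fraction who "experience at least a 30% decline from the maximum to the minimum PSA value while on study".
- **Section 10.2**, on sample size, uses the same form over a different period: "decline from their maximum PSA anytime during treatment to the minimum value during treatment".
- **Section 10.1.1** states the primary objective as a "confirmed 30% decline in PSA in a modest fraction of participants enrolled".
- **Section 6.3.2** gives the detailed rule. The apex is the highest PSA that another on-study value matches within 10%. Then: "Responders will then be evaluated using confirmed PSA declines (at least 2 consecutive values after the intra-study apex) of at least 30" percent. The stated purpose is to keep isolated laboratory spikes out.
- **Section 3.1** allows PSA values from before enrolment to count: "the 3 PSA values obtained prior to enrollment will be evaluated as if they were collected during the surveillance period". It ties them to the apex and refers to 6.3.2. It does not say whether they may supply the lowest value.

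Sections 10.2, 10.4.1 and 10.4.2 do not refer to 6.3.2, and nothing says which text governs.

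**The concern.** This is the only primary efficacy endpoint of an open-label trial whose primary analysis is single-arm. The 15% null, the 35% target and the 7/25 illustration can be interpreted only under one fixed response rule. The operative analysis text drops three safeguards found in 6.3.2 (validated apex, values after the apex, two consecutive values), and the period runs over treatment in one place and over the whole time on study in another. One PSA series could therefore be a response under one section and not under another, and the choice could be made after the data are seen.

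**Working it through.** **1. The plan's own figures.** Inputs from 10.2: n = 25, p0 = 0.15, p1 = 0.35, one-sided 0.10, exact binomial. The smallest admissible cutoff is 7, since P(X≥6 | 25, 0.15) = 0.162 and P(X≥7 | 25, 0.15) = 0.0695. Power is P(X≥7 | 25, 0.35) = 0.827, against the stated 82%. The exact one-sided 90% bounds for 7/25 are 16.3% and 42.6%, as stated. The design arithmetic is sound; the open question is which endpoint it applies to.

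**2. The definitions side by side.**

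| | 6.3.2 | 10.1.1 | 10.2 | 10.4.1 / 10.4.2 |
|---|---|---|---|---|
| Confirmation | 2 consecutive values | confirmed, no detail | none | none |
| Apex validated within 10% | yes | not stated | no | no |
| Low value after high value | explicit | not stated | not explicit | not explicit |
| Window | on study | not stated | treatment | on study |

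**3. Ordered reading of 10.4: effect of noise.** The PSA schedule comes from the study calendar (section 18.1, 28-day months): M-4 to M-1, C1D1, C1D15, C2D1 to C7D1 and end of treatment, or 13 values over 308 days. Doubling times of 5-15 months come from section 2.1.3.3. Assumptions not in the documents: exponential growth unchanged by treatment, doubling times uniform on 5-15 months, and independent lognormal within-patient noise. Without noise, a rising PSA gives no ordered fall, so 0% respond. With noise, the simulated false-responder rates are:

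| Assumed CV | Later minimum ≥30% below the on-study maximum, unconfirmed | 6.3.2 rule |
|---|---|---|
| 5% | 0% | 0% |
| 10% | about 0.5% | about 0.03% |
| 15% | about 9% | about 0.8% |
| 20% | about 25% | about 4% |

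Using only the values from C1D1 to end of treatment, the CV 20% rates are 24.5% and about 3%.

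In the 7/25 rule, a false rate of 9.1% gives P(X≥7) = 0.006. A rate of 24% gives 0.39, and 24.9% gives 0.43. The value at the 15% null is 0.0695.

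**4. Literal unordered reading, (max − min)/max.** A pure rise reaches 30% once PSA has grown by 1/0.7 = 1.429-fold, which is log2(1/0.7) = 0.515 doublings. The longest doubling time that scores is the window in months divided by 0.515:

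- C1D1 to end of treatment: 196 days = 6.44 months; 6.44/0.515 = 12.5 months. Uniform share: (12.5 − 5)/10 = 75%.
- M-4 to end of treatment, full surveillance: 308 days = 10.12 months; limit 19.7 months, so 100% of the eligible range.

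**5. Does the design fit the unordered reading?** Section 10.2 assumes that 10% of surveillance controls reach the 30% change in 6 months. If growth counted, every control with a doubling time up to 6.0/0.515 = 11.7 months would score. That is (11.7 − 5)/10 = 67% on the uniform assumption, taking the control trial's range to be the same.

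**The case against.** A reader might infer that 10.4 scores any maximum-minus-minimum difference, so that ordinary untreated PSA growth counts as success and an inactive vaccine would pass. The documents do not support that. Sections 10.2, 10.4.1 and 10.4.2 all speak of a decline from the maximum to the minimum, and a steady rise is not a decline. The planned 15% null and 10% control rate fit a true fall, not the 67% to 100% that growth alone would produce. Order and confirmation are missing from 10.4, not from the plan: 6.3.2 supplies both and 10.1.1 says confirmed. Section 3.1 links pre-enrolment values to the apex only, and since the 05/10/2023 amendment surveillance may be shorter than the full period behind the 308-day figure.

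The noise argument is also conditional. The CVs are assumed, and at 15% or less the false rate stays below the null.

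All of this stands, and it limits the size of the point. It does not remove the conflict. The primary analysis text omits safeguards that the protocol defines and does not cite them. Section 10 also speaks more loosely of a 30% PSA change, so the order should be explicit.

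**Conclusion.** The primary endpoint is defined inconsistently in confirmation, apex validation, explicit order and window. That follows from the text and needs no assumption. Its numerical effect depends on PSA variability. Under the natural, ordered reading of 10.4 the excess of false responders over 6.3.2 is negligible at CV 10%, about 8 percentage points at 15% and about 21 at 20%. Only the last would undermine the 7/25 rule, with a 0.39 to 0.43 chance of reaching it without any treatment effect. These rates rest on the growth, doubling-time and noise assumptions above. The 75% and 100% figures describe a literal unordered computation only. They are a reason to exclude that computation in the text, not a forecast of how the trial would be analysed.

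**What to change.** - In 10.2, 10.4.1 and 10.4.2, replace the maximum-to-minimum wording with a reference to the 6.3.2 confirmed response.
- State that the declining values must come after the apex.
- Reconcile the treatment and on-study periods into one prespecified window, in which surveillance or pre-enrolment values cannot supply the nadir. This last condition goes beyond 6.3.2, so the sponsor would have to adopt it explicitly.
- Keep the maximum-to-minimum change as a descriptive display only.

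The edit itself is protocol and SAP wording, with no new visits or samples. The cost is statistical: a confirmed rule may give a lower observed response rate. The 82% power carries over only if 35% is the target for the confirmed endpoint. If the true confirmed rate were 30%, the power of the 7/25 rule would be P(X≥7 | 25, 0.30) = 0.66. The sponsor should state that 15% and 35% refer to the confirmed response, or revisit them.
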